8.4 Informed consent

The Investigator will:

- Ensure each subject is given full and adequate oral and written information about the nature, purpose, and possible risk of the study.
- Ensure each subject is notified they are free to discontinue from the study at any time.
- Ensure each subject is given the opportunity to ask questions and allowed time to consider the information provided.
- Ensure each subject provides signed and dated informed consent before conducting any procedure specifically for the study.
- Ensure the original, signed ICF is/are stored in the Investigator's Study File.
- Ensure a copy of the signed ICF is given to the subject.
- Ensure any incentives for subjects who participate in the study as well as any provisions for subjects harmed as a consequence of study participation are described in the informed consent form that is approved by the IRB.

8.5 Changes to the protocol and informed consent form

Study procedures will not be changed without the mutual agreement of the Investigator and AstraZeneca.

If there are any substantial changes to the study protocol, then these changes will be documented in a study protocol amendment and where required in a new version of the study protocol (Revised Clinical Study Protocol).

The amendment is to be approved by the IRB and if applicable, also the national regulatory authority approval, before implementation. Local requirements are to be followed for revised protocols.

AstraZeneca will distribute any subsequent amendments and new versions of the protocol to each Investigator(s). For distribution to the IRB see Section 8.3.

If a protocol amendment requires a change to a center's ICF, AstraZeneca and the center's IRB are to approve the revised ICF before the revised form is used.

If local regulations require, any administrative change will be communicated to or approved by the IRB.

8.6 Audits and inspections

Authorized representatives of AstraZeneca, a regulatory authority, or the IRB may perform audits or inspections at the center, including source data verification. The purpose of an audit or inspection is to systematically and independently examine all study-related activities and documents, to determine whether these activities were conducted, and data were recorded, analyzed, and accurately reported according to the protocol, GCP, guidelines of the ICH, and any applicable regulatory requirements. The Investigator will contact AstraZeneca immediately if contacted by a regulatory agency about an inspection at the center.

9. STUDY MANAGEMENT BY [REDACTED]

[REDACTED] will be managing the study on behalf of AstraZeneca.

9.1 Pre-study activities

Before the first subject is entered into the study, it is necessary for a representative of [REDACTED] or designee to visit the investigational study site to:

- Determine the adequacy of the facilities
- Determine availability of appropriate subjects for the study
- Discuss with the Investigator(s) (and other personnel involved with the study) their responsibilities with regard to protocol adherence, and the responsibilities of AstraZeneca or its representatives. This will be documented in a Clinical Study Agreement (CSA) between AstraZeneca and the Investigator.

9.2 Training of study site personnel

Before the first subject is entered into the study, an [REDACTED] representative will review and discuss the requirements of the CSP and related documents with the investigational staff and also train them in any study specific procedures system(s) utilized.

The Investigator will ensure appropriate training relevant to the study is given to all of these staff, and any new information relevant to the performance of this study is forwarded to the staff involved.

The Investigator will maintain a record of all individuals involved in the study (medical, nursing and other staff).

9.3 Monitoring of the study

During the study, an AstraZeneca/[REDACTED] representative will have regular contacts with the study site, including visits to:

- Provide information and support to the Investigator(s)

- Confirm that facilities remain acceptable
- Confirm that the investigational team is adhering to the protocol, that data are being accurately and timely recorded in the pCRFs, that biological samples are handled in accordance with the Laboratory Manual and, study drug accountability checks are being performed
- Perform source data verification (a comparison of the data in the CRFs with the subject's medical records at the hospital or practice, and other records relevant to the study) including verification of informed consent of participating subjects. This will require direct access to all original records for each subject (eg, clinic charts)
- Ensure withdrawal of informed consent to the use of the subject's biological samples is reported and biological samples are identified and disposed of/destroyed accordingly, and the action is documented and reported to the subject.

The AstraZeneca [REDACTED] representative will be available between visits if the Investigator(s) or other staff at the center needs information and advice about the study conduct.

9.3.1 Source data

Refer to the CSA for location of source data.

9.4 Study agreements

The Investigator should comply with all the terms, conditions, and obligations of the CSA, or equivalent, for this study. In the event of any inconsistency between this CSP and the CSA, the terms of CSP shall prevail with respect to the conduct of the study and the treatment of subjects and in all other respects, not relating to study conduct or treatment of subjects, the terms of the CSA shall prevail.

Agreements between AstraZeneca and the Investigator should be in place before any study-related procedures can take place, or subjects are enrolled.

9.4.1 Archiving of study documents

The Investigator follows the principles outlined in the CSA.

9.5 Study timetable and end of study

The end of the study is defined as 'the last visit of the last subject undergoing the study'.

The study is expected to start in the [REDACTED] and to end by the [REDACTED].

The study may be terminated at individual centers if the study procedures are not being performed according to GCP, or if recruitment is slow. AstraZeneca may also terminate the

entire study prematurely if concerns for safety arise within this study or in any other study with TC-5214.

10. DATA MANAGEMENT BY [REDACTED]

Data management will be performed by [REDACTED] Phase I Data Management.

When the completed pCRFs have been scanned and indexed, the data are entered into the study database and proofread.

The study Data Management Plan (DMP) will describe the methods used to collect, check and process clinical data in detail. It will also clarify the roles and responsibilities for the different functions and personnel involved in the data management process. Furthermore, the DMP will describe the data flow and timelines within the study.

Paper CRFs or electronic case report forms (eCRF)s will be used to record all data except from bioanalysis concentration data and safety lab data or any other data that will be transferred electronically from an external source. For pCRFs data should be recorded legibly onto the pCRFs in blue or black ballpoint pen. Correction fluid or covering labels must not be used.

Paper CRF and eCRF operations are following [REDACTED] Standard Operation Procedures (SOPs) and data is processed in validated CFR 21 Part 11 compliant systems. Screening failures (subjects who signed consent to take part in the study but were not allocated a screening number) will not be entered into the clinical study database.

In the case of genotypic data, only the date the subject gave consent to participation in the genetic research and the date the blood sample was taken from the subject will be recorded in the pCRF and database.

Some or all of the clinical datasets from the main study may be merged with the genetic data in a suitable secure environment separate from the clinical database. The results from this genetic research will be reported separately from the CSR for the main study.

Data storage will be done in accordance with AstraZeneca/GCP guidelines.

11. EVALUATION AND CALCULATION OF VARIABLES BY [REDACTED]

11.1 Calculation or derivation of safety variable(s)

All AEs will be collected for each subject from the time when informed consent is obtained (Visit 1) until the follow-up visit (Visit 3). AEs that occur before dosing will be reported separately.

Change-from-baseline variables will be calculated by [REDACTED] Inc for the safety variables listed below, as the posttreatment value minus the value at baseline. The baseline values will be as follows:

- Clinical laboratory tests: Day -1 value
- Vital signs (including supine blood pressure and pulse): Day -1 time-matched values
- ECG: Day 1

Baseline values for safety variables during each respective period will serve as the baseline value for that period.

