1.4 Benefit/risk and ethical assessment

There will be no benefit for subjects participating in this study. Given the observed pharmacological and toxicological profiles in nonclinical studies and previous clinical experience, it is judged that TC-5214 can be given in carefully monitored clinical trials.

The doses selected for subjects with moderate and severe renal impairment have been reduced to a single dose well below the highest single doses shown to be safe and well tolerated in healthy subjects.

Inclusion and exclusion criteria as well as study restrictions are chosen to ensure that the selected subjects are exposed to minimal risk.

The major risk for subjects who participate in the study is from AEs induced by TC-5214. The most likely safety concern for subjects receiving TC-5214 will be orthostatic hypotension, based on clinical data on mecamylamine and its mechanism of action. Orthostatic hypotension may occur when vascular volume is depleted, for example when fluid is withdrawn during the dialysis session. A low TC-5214 dose of 2 mg has been chosen for these subjects as an additional measure of safety.

There is a slight risk of infection or bruising that may occur as a result of phlebotomy. Treatment-emergent adverse events in the previous SAD study included vertigo, decreased neutrophil count, and somnolence in the TC-5214 4 mg group; vertigo in the TC 5214 8 mg group; nausea, xerosis, dizziness, eating disorder, and decreased appetite in the TC-5214 16 mg group. For further information regarding an overall risk benefit assessment, see [Investigator's Brochure TC-5214](#).

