Height and weight ^a	X	X						X		6.3.6
Medical and Surgical History	X									6.2
Columbia Suicide Severity Rating Scale	X	X						X	X	6.2
Clinical chemistry	X	X						X	X	6.3.5
Hematology	X	X						X	X	6.3.5
Urinalysis	X	X						X	X	6.3.5
HIV and HBV Serology	X									6.3.5
Drugs of Abuse Screen	X	X								6.3.5
Alcohol Screen		X								6.3.5
Blood pregnancy test for female subjects of childbearing potential	X	X						X		6.3.5

Visit number	1	2 Residential Period							3	
Activity/ Day	-30 to -2 Screening	-1^h	1	2	3	4	5	6	Follow-Up 7 to 10 days following discharge	Details in Section
Orthostatic blood pressure (supine, seated, and standing) and pulse ^b	X	X	X	X	X	X	X	X	X	6.3.7
Oral temperature and respiration rate	X	X	X	X	X	X	X	X	X	6.3.5
12-lead ECG ^c	X	X	X					X	X	6.3.6.1
Admission to the clinic		X								NA
Pharmacogenetic sampling (optional) ^j		X								6.5.1
TC-5214 administration ^d			X							5.5.2
Blood sample collection for PK ^e			X	X	X	X	X	X		6.4.1.1
Urine sample collection for PK ^f			X	X	X	X	X	X		6.4.1.2
Dialysis Period			X			X				6.4.1.4
Dialysate Collection						X ^j				6.4.1.4
Discharge from clinic								X ^g		NA
Concomitant medications	X	X	X	X	X	X	X	X		5.6
Adverse Events	X	X	X	X	X	X	X	X	X	6.3

- a Height will be measured during the screening visit only.
- b Orthostatic blood pressure and pulse will be measured at the Screening Visit, on Day -1 (time to correspond with the planned predose and 4 hour postdose timings for Day 1), on Day 1 at predose and 4 hours postdose, each morning during the residential period and at the Follow-up Visit.
- c Subjects must rest in the supine position for 10 minutes prior to the 12-lead ECG evaluation to be performed at screening, on admission on Day -1, on Day 1 at 4 hours postdose, before discharge on Day 6, and at the Follow-up Visit.
- d Study drug will be administered with 240 mL room temperature water.
- e For detailed timings of blood PK sampling times see Section 6.4.1.1.
- f Urine collection times: Urine samples for PK will be collected for 120 hours postdose in the following intervals: 0-12, 12-24, 24-48, 48-72, 72-96, and 96-120 hours. Urine will be collected for subjects in Part 2 for Groups 1 through 3, and for subjects in Group 5 who produce urine.
- g Subjects will be discharged from the unit after all study procedures have been completed.
- h Subjects may be admitted to the clinic on Day -2 for the Day -1 assessments at the discretion of the Investigator.
- i Abbreviated physical examination.

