For SAEs causal relationship will also be assessed for other medication and study procedures. Note, for SAEs that could be associated with any study procedure the causal relationship is implied as ‘yes’.

A guide to the interpretation of the causality question is found in [Appendix B](#) to the Clinical Study Protocol.

Adverse events based on signs and symptoms

All AEs spontaneously reported by the subject or reported in response to the open question from the study personnel: “Have you had any health problems since the previous visit/you were last asked?”, or revealed by observation will be collected and recorded in the CRF. When collecting AEs, the recording of diagnoses is preferred (when possible) to recording a list of signs and symptoms. However, if a diagnosis is known and there are other signs or symptoms that are not generally part of the diagnosis, the diagnosis and each sign or symptom will be recorded separately.

Adverse events based on examinations and tests

The results from protocol mandated laboratory tests and vital signs will be summarized in the clinical study report (CSR). Deterioration as compared to baseline in protocol-mandated laboratory values, vital signs, ECGs, and other safety assessments should therefore only be reported as AEs if they fulfill any of the SAE criteria or are the reason for discontinuation of treatment with the IP or if the Investigator insists on reporting them as an AE.

If deterioration in a laboratory value/vital sign is associated with clinical signs and symptoms, the sign or symptom will be reported as an AE and the associated laboratory result/vital sign will be considered as additional information. Wherever possible the reporting Investigator uses the clinical, rather than the laboratory term (eg, anaemia versus low hemoglobin value). In the absence of clinical signs or symptoms, clinically relevant deteriorations in non-mandated parameters should be reported as AE(s).

Deterioration of a laboratory value, which is unequivocally due to disease progression, should not be reported as an AE/SAE.

Any new or aggravated clinically relevant abnormal medical finding at a physical examination as compared with the baseline assessment will be reported as an AE.

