6.3.7.1 Pulse and blood pressure

Blood pressure (BP) and pulse (supine, seated, and standing) will be measured using a semi-automatic BP recording device with an appropriate cuff size. The volunteers will be required

to rest in a supine position for at least 10 minutes prior to BP and pulse rate measurements. For the seated evaluation, volunteers will be required to be in the sitting posture for at least 2 minutes for BP and pulse. For the standing evaluation, volunteers will be required to be in the upright standing posture for at least 3 minutes respectively for BP and pulse.

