12.2.2 Safety

All safety data (scheduled and unscheduled) will be presented in the data listings.

Safety variables (ie, clinical laboratory values, vital signs, and ECGs) will be reported to the same precision as the source data. Derived variables will be reported using similar precision to those from which they were derived (eg, QT_c derived from QT interval).

Extra measurements (such as unscheduled or repeat assessments) will not be included in the descriptive statistics, but will be included in data listings. All AEs, ECG outliers, and clinical laboratory outliers that occur following the first dose of study medication will be included in the tabulations of AEs and outlier events, including episodes that occur at unscheduled evaluations.

All available data from subjects in the safety analysis set will be included in the safety analyses. No adjustment or imputation will be utilized for missing values or for subjects who withdraw prior to completing the study, neither will analyses be restricted to subjects with complete data.

All AEs will be collected for each subject when informed consent is obtained (Visit 1) until the follow-up visit (Visit 3). AEs that occur before dosing will be reported separately.

AEs will be summarized by preferred term and system organ class using MedDRA vocabulary (version 12.0 or higher) by treatment and across all treatments. Furthermore, listings of SAEs and AEs that led to withdrawal will be made and the number of subjects who had any AEs, SAEs, AEs that led to withdrawal, and AEs with severe intensity will be summarized.

Tabulations and listings of data for vital signs, clinical laboratory tests, ECGs, and physical examination findings will be presented. All continuous safety data will be summarized across all treatments for the absolute value at each scheduled assessment and for the corresponding change from baseline. For clinical laboratory tests, listings of values for each subject will be presented with abnormal or out-of-range values flagged. Clinical laboratory data will be reported in Système International units in the CSR.

For ECG parameters, the QT correction factor will be based on the Fridericia's formula. Further categorical summaries of absolute QT and QTcF values (greater than 450 ms, greater than 480 ms, greater than 500 ms) and change-from-baseline values in QT and QTcF values (greater than 30 ms, greater than 60 ms) may also be produced.

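### No within-subject postural blood pressure change or count of postural falls is defined, so asymptomatic orthostatic falls are not systematically counted by renal group

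*Supplement*

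**What the plan says.** Protocol section 1.4: "The most likely safety concern for subjects receiving TC-5214 will be orthostatic hypotension, based on clinical data on mecamylamine and its mechanism of action".

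Section 6.3.7.1: "Blood pressure (BP) and pulse (supine, seated, and standing) will be measured using a semi-automatic BP recording device", with a set minimum time in each posture (10 minutes supine, 2 seated, 3 standing). The study plan tables in section 3.1 label the assessment as orthostatic. They schedule it at screening, on Day -1 at clock times matching the Day 1 predose and 4-hour readings, and then "on Day 1 at predose and 4 hours postdose, each morning during the residential period and at the Follow-up Visit".

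Section 11.1 defines change-from-baseline variables "as the posttreatment value minus the value at baseline". For vital signs the baseline is "Vital signs (including supine blood pressure and pulse): Day -1 time-matched values". Only the supine position is named, but the word before it means that the other positions are not excluded.

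Section 12.2.2: "All continuous safety data will be summarized across all treatments for the absolute value at each scheduled assessment and for the corresponding change from baseline". The same section tabulates outlier events for ECG and laboratory data, and allows optional categorical summaries for QT and QTcF. It has no counterpart for blood pressure.

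Section 6.3.3 says that deterioration in protocol-mandated vital signs "should therefore only be reported as AEs if they fulfill any of the SAE criteria or are the reason for discontinuation of treatment", or if the Investigator insists. If symptoms accompany the deterioration, the sign or symptom is the adverse event.

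**The concern.** The readings needed for a baseline-adjusted postural change are collected by design: three positions, at matched times before and after dosing. The analysis treats each position as a separate series. The quantity that defines an orthostatic effect is the difference between standing and supine in one subject at one time, and it is not derived. No criterion is applied to it and no subjects are counted.

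At stake is the secondary objective of comparing safety and tolerability in renal impairment with controls. For the risk the sponsor thinks most likely, a reader of the report could not see from a planned table how many subjects in each group had a postural fall, or how many of those falls were new after dosing.

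**Working it through.** The plan states no figure on this point, so there is none to reproduce. The check sets the sections side by side; two small examples with assumed numbers then show what the planned summaries can and cannot reveal.

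**1. Where a postural fall can surface under the plan**

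| Type of fall | Route in the plan | Counted by a set criterion? |
|---|---|---|
| Symptomatic | Adverse event as symptom, or as diagnosis where possible (6.3.3); tabulated by preferred term (12.2.2) | Counted as an adverse event |
| Serious, or reason for discontinuing | Adverse event (6.3.3) | Counted as an adverse event |
| Asymptomatic, Investigator insists | Adverse event (6.3.3) | Depends on the Investigator |
| Asymptomatic, non-serious, not reported | Listings and by-position summaries (12.2.1, 12.2.2); medical review for other significant adverse events (11.1.1) | No |

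The last row is the gap.

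**2. What by-position summaries recover**

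With complete data in the same subjects, mean postural change = mean standing value - mean supine value, so the group mean can be recovered. The spread of the postural change and the number of subjects beyond a threshold cannot, because they need the difference within each subject.

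**3. Example A (assumed numbers)**

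Eight subjects. Standing systolic change from Day -1 is -28 mmHg in two and 0 in six. Supine values are unchanged, and there was no postural difference on Day -1.

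- Mean = (2 x -28 + 6 x 0)/8 = -7 mmHg.
- SD = sqrt[(2 x 21^2 + 6 x 7^2)/7] = sqrt(1176/7) = 13.0 mmHg.
- Median 0, minimum -28, maximum 0.
- Subjects affected: 2/8 = 25%.

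Section 12.2.1 requires mean, SD, median, minimum and maximum, so the -28 would be visible. The table would not state how many subjects fell.

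**4. Example B (assumed numbers)**

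Change in postural difference = standing change - supine change, both from the matched Day -1 time.

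- Subject 1: standing -28, supine -28. Result: -28 - (-28) = 0 mmHg, no postural effect.
- Subject 2: standing -28, supine 0. Result: -28 - 0 = -28 mmHg.
- Subject 3: standing -12, supine +12. Result: -12 - 12 = -24 mmHg.

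Subjects 1 and 2 look the same in the standing summary. Subject 3 shows a change of only 12 mmHg in either position, yet has a postural change of 24 mmHg.

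**5. Why the Day -1 difference matters for the group comparison**

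Exclusion criterion 24 lists beta blockers, vasodilators and calcium channel blockers as not accepted in controls. Criterion 25 allows them in renally impaired subjects at the Investigator's discretion. Postural falls before dosing may therefore differ between groups. Subtracting the matched Day -1 postural difference separates these from falls that are new after dosing.

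**The case against.** A reader might infer that orthostatic hypotension is counted nowhere, or that 6.3.3 excludes most falls. The documents support neither. Symptomatic, serious, discontinuing and Investigator-reported falls reach the adverse event tables, and the plan gives no figure for the share of falls without symptoms. Section 11.1.1 also provides a medical review of vital-sign data, and all safety data are listed. With about 32 subjects, individual readings can be inspected. A reader might also infer that the tables would show only an unremarkable mean; example A shows that the minimum and SD would draw attention.

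Nor should the contrast with ECG data be pressed: the QT and QTcF categories are optional. Outlier tabulation for ECG and laboratory data, but not vital signs, is still a real difference.

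No separate statistical analysis plan is shown, and such a derivation could sit there. That has weight. But 11.1 and 12.2.2 do set out safety derivations and summaries, down to millisecond categories for QTcF, and leave this one out.

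Finally, the analysis is descriptive, with 8 subjects planned per group. Groups 1 and 2 receive 8 mg and Groups 3 and 5 receive 2 mg (5.5.2), so a count by group could not isolate the effect of renal impairment. The data are collected anyway, so the derivation could be run at reporting. These points limit the weight of the finding. They do not remove it: a listing or expert review without a criterion is not a systematic count, and a criterion chosen after the readings are seen carries less weight.

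**Conclusion.** The concern holds in a limited form. The plan defines no within-subject postural change and no count of postural falls, although this is its named most likely safety concern and the readings are taken. Followed as written, it would not systematically count asymptomatic, non-serious falls by renal group; they would show only in listings, by-position summaries and a judgement-based review.

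The size cannot be stated from the documents, which give no incidence of postural falls and no threshold. The examples rest on assumed numbers and show only the mechanism. This is a worthwhile improvement to the safety analysis; it does not touch the primary pharmacokinetic objective or suggest that safety is otherwise unassessed. The conclusion assumes that no separate analysis plan already supplies the derivation.

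**What to change.** In 11.1, derive standing minus supine systolic pressure, diastolic pressure and pulse at each scheduled time. Also derive the change from the Day -1 time-matched postural difference where a matched time exists. Matching is scheduled only for the predose and 4-hour readings, so say what serves as baseline, if anything, for the later mornings and follow-up.

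In 12.2.2, summarize these variables by renal function group. Say so explicitly, because the current sentence on continuous safety data speaks of summaries across all treatments. Tabulate the number of subjects in each group who meet a postural-fall criterion that the sponsor fixes in advance, separating falls already present on Day -1 from new post-dose falls. A fall of 20 mmHg systolic or 10 mmHg diastolic is only an assumed example; the documents give no value.

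The cost is a few derived variables, their summary and one count table, all from data already collected. No visit, site procedure or dose changes.
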